### **Saliva Collection and pH Measurement:**

Salivary samples will be collected from the participants. At the first stage,

participants will be given a paraffin wax to chew, which stimulates saliva production, and they will be asked to swallow the pooled saliva. Then, they will be instructed to spit their saliva into a saliva-collecting tube for five minutes. At each designated time point, the pH of saliva will be measured using pH test strips. The strips will be soaked in the saliva for one minute, and the resulting color change, indicating pH values, will be recorded by comparing it with the accompanying reference chart (**Alkarad, Alkhouri and Dashash, 2023; Campus et al., 2024**).

- **Patient compliance:** monitored with a diary and product usage checks.

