### **Secondary Objectives:**

1. To assess oral health status using Gingival Bleeding Index (GBI), and Plaque

Index (PI).

2. To measure salivary pH changes over the study period.

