### **Blinding:**

This study will be conducted under a double-blind design. Both the principal investigator and the participants will be blinded to group allocation. The toothpaste and mouthwash bottles will be coded and identical in appearance, color, and packaging, ensuring that neither the clinician nor the participant can identify which formulation (hydroxyapatite-containing or conventional) is being used. The code will be kept by an independent researcher who is not involved in the study procedures or data analysis and will only be revealed after the completion of data collection.

All clinical assessments, including Gorelick Index (GI), Diagnodent Pen measurements, digital photography, Gingival Bleeding Index (GBI), Plaque Index (PI), and salivary pH, will be conducted without knowledge of participants' assigned group.

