## **Inclusion Criteria:**

All included participants will be drawn from those who will receive comprehensive orthodontic treatment and fulfill the following inclusion criteria:

1. Complete permanent dentition up to the first premolar, with no intended extractions in orthodontic treatment plan.
2. Good overall health.
3. Good oral hygiene: full-mouth plaque score < 20%.
4. No bleeding upon probing after 30 seconds.
5. Discontinuous band of plaque at the gingival margin.
6. Normal stimulated salivary flow rate.
7. Normal buffer capacity (final pH between 6.0 and 7.0).

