### **Sample Size:**

The sample size for the present study was determined to provide 80% statistical power at a 5% significance level ( $\alpha = 0.05$ ) to detect a 1-unit difference in the decalcification index (Gorlick index) (**Hoffman et al, 2014**). Accordingly, the current study will include a total of 75 participants, equally distributed into three groups of 25 subjects each, to ensure adequate statistical power and to account for potential dropouts.

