### Assessment of White Spot Lesions Using DIAGNOdent Pen:

In this study, the cutoff values of the DIAGNOdent device will be adopted according to the manufacturer's operating guide to standardize data collection in the clinical

setting. Readings from 0–10 represent sound tooth structure, 11–20 indicate outer half enamel caries, 21–30 correspond to inner half enamel caries, and readings of  $\geq 30$  are considered dentin caries (**KaVo Dental, Biberach an der Riss, Germany**). These values will serve as a reference for monitoring changes in white spot lesions during the study (**Du et al., 2011; Gohar, Ibrahim and Safwat, 2023**).

Prior to each measurement, the device will be calibrated for every patient. Readings will be obtained from four locations on the labial/buccal surface of each tooth: gingival, occlusal, mesial, and distal, in accordance with the recommendation of (Banks & Richmond, 1994). After drying the tooth surface, the number 2 pen tip will be placed 1 mm from the bracket on the labial surface of the tooth being examined.

The baseline measurement (T0) will be recorded in the patient's dental chart. Subsequent assessments will be performed at 1, 3, and 6 months (T1, T3, and T6) after the placement of the orthodontic appliance. All measurements will be conducted by a single trained examiner to ensure consistency and reliability.

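### Salivary pH is taken from a single by-eye match of a test strip to a colour chart, with no stated strip graduation, duplicate reading or reader calibration; a pH meter would be a cheap gain in precision

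*Protocol*

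**What the plan says.** The second item under Secondary Objectives is "To measure salivary pH changes over the study period". The section Saliva Collection and pH Measurement fixes the method. Saliva is stimulated by chewing paraffin wax and collected for five minutes, and at each time point "the pH of saliva will be measured using pH test strips". The strip is soaked for one minute and then read by eye: "the resulting color change, indicating pH values, will be recorded by comparing it with the accompanying reference chart". Two published studies are cited for the procedure. Strip brand, range and step size are not given, and nothing is said about who reads the strip, whether readers are calibrated or whether a reading is repeated.

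Other outcomes have safeguards that pH lacks. For the DIAGNOdent pen the device is calibrated for every patient, and "All measurements will be conducted by a single trained examiner to ensure consistency and reliability". For the photographs a single investigator takes all the images. The Blinding section includes salivary pH among the assessments that "will be conducted without knowledge of" the assigned group.

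**The concern.** The objective is to track change, so each participant's result is a difference between readings, and each reading carries two errors: rounding to the nearest chart colour, and the reader's judgement of which colour is nearest. Neither can be removed at the analysis. The trial is multicentre, so more than one person may read strips unless the protocol says otherwise.

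At stake is the interpretation of a null result. If no pH difference between arms is found, the reader of the thesis cannot tell whether there was none or whether the instrument was too insensitive to show it. The sample size does not help, since it was set "to detect a 1-unit difference in the decalcification index (Gorlick index") and says nothing about pH.

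**Working it through.** **The plan's own figure.** The protocol has no pH calculation to reproduce. Its one sample size, 25 per group, is for the Gorelick index at "80% statistical power at a 5% significance level". With a difference of 1 and a two-sided test (assumed), n = 2(1.96 + 0.84)² × SD² / 1² ≈ 15.7 × SD², so 25 per group corresponds to an SD of about 1.26 before any dropout allowance. The protocol states neither the SD nor a dropout rate, and the figure has no bearing on pH.

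**Inputs.** From the protocol: 25 per arm; 5% significance level. Assumed, because the protocol does not give them: between-person SD of pH s = 0.3 or 0.4; true difference between two arms 0.25; strip step w = 0.2, 0.5 or 1.0; reader SD r = 0, or 0.25 for illustration.

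**Formula.** Rounding to a step w adds a variance of about w²/12, and reader error adds r²:

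total SD = √(s² + w²/12 + r²)

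standard error of the arm difference = total SD × √(2/25)

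power ≈ Φ(0.25 / standard error − 1.96)

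**Worked case, s = 0.3, w = 0.5, r = 0.** Total SD = √(0.09 + 0.0208) = 0.333. Standard error = 0.333 × 0.283 = 0.094. Power ≈ Φ(2.655 − 1.96) = Φ(0.695) ≈ 76%. A simulation with real rounding and a t-test gives 74%. The normal approximation runs slightly high, so the simulated values are used below.

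**Simulated power without reader error** (20,000 runs per cell, 25 per arm, values rounded to the step with the mean at a random position, two-sided t-test, difference 0.25):

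| Step | Variance added at SD 0.3 | Power, SD 0.3 | Power, SD 0.4 |
|---|---|---|---|
| continuous | 0% | 82% | 58% |
| 0.2 | 4% | 81% | 57% |
| 0.5 | 23% | 74% | 53% |
| 1.0 | 93% | 55% | 43% |

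**Reader error.** With an assumed reader SD of 0.25 at s = 0.3, power falls to about 59%, 54% and 44% for steps of 0.2, 0.5 and 1.0. For a fine strip, the reader therefore matters more than the step.

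**What the remedies recover.** Recording to 0.1 adds 0.1²/12 = 0.0008 to a variance of 0.09, which is under 1%. Averaging two independent readings halves the reader variance from 0.0625 to 0.0313. With 0.2-unit strips and s = 0.3, total SD falls from √(0.09 + 0.0033 + 0.0625) = 0.395 to √(0.09 + 0.0033 + 0.0313) = 0.353, and approximate power rises from 61% to 71%.

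**Limit of the check.** It compares one reading per participant between two arms. For a change from baseline, rounding enters at both visits and adds about w²/6. If 0.3 is the SD of the change, a 0.5-unit strip gives √(0.09 + 0.0417) = 0.363 and an approximate power of 68%, against 76% for a single reading by the same formula. The single-reading figures therefore do not exaggerate the loss for a change score with the same SD.

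**The case against.** The strongest reply is that this is a preference and not an error. Nothing in the protocol is contradicted, pH is the last-listed secondary objective, no power is claimed for it, and the method is referenced to two studies. The Settings section also commits sample collection to standardised procedures at all sites, and strips are used at every time point, so the instrument does not change between visits. All of that stands, and it keeps the point small.

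The numerical inputs are also open to challenge, because SD, effect and step are all assumed. Moving the SD from 0.3 to 0.4 costs about 24 points of power (82% to 58%), more than a 0.5-unit strip does (about 8 points at SD 0.3 and 5 at SD 0.4). That is fair: before reader error, only the 1.0-unit case at SD 0.3 costs more than the uncertainty in the SD.

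Three stronger readings are tempting, and the documents do not support them:

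- **That the scale is coarse.** The step size is not stated. The protocol is compatible with 0.2-unit strips, for which rounding alone costs almost nothing.
- **That the expected change is only a fraction of a pH unit.** A reader might infer this from the entry criterion "Normal buffer capacity (final pH between 6.0 and 7.0"). That criterion concerns buffer capacity at entry, not the pH of stimulated saliva measured later, and the protocol gives no expected change or SD for pH.
- **That a subjective reading threatens the fairness of the comparison.** The pH assessment is blinded, so reader error is mainly noise. Nor is a colour match shown to be more subjective than grading lesion surface, plaque thickness or bleeding, which are also judged by eye.

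What survives is that the by-eye method is fixed in the protocol without the reader safeguards given to the photographs and the DIAGNOdent pen, and that a more precise reading of the same sample is readily available.

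**Conclusion.** The point holds as a cheap improvement to the precision of a secondary outcome. A single visual strip reading, with no stated graduation, repeat or reader calibration, can only add noise. Under the assumed difference of 0.25 and SD of 0.3 to 0.4 with 25 per arm, the loss of power from rounding alone runs from about 1 point (0.2-unit steps) through 5 to 8 points (0.5) to 15 to 27 points (1.0), with more lost if readers vary. Where this trial lies in that range cannot be determined from the protocol. The primary outcomes and the stated sample size are unaffected, and there is no ground to expect bias between arms.

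**What to change.** In Saliva Collection and pH Measurement, replace the strip reading with a handheld digital pH meter used on the same five-minute sample, calibrated at each session and recorded to at least 0.1. State that the same method applies at baseline, at 1, 3 and 6 months, and at all sites.

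If strips are kept, specify narrow-range strips with steps of 0.2 or finer, state the graduation, and record the mean of two readings per sample.

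The cost is one small purchase per site where pH is read (meter and buffer solutions, or finer strips), which matters somewhat in a self-funded trial, and a short calibration per session. No extra sample, visit or staff is needed. The change should be made before the first baseline reading so that all visits share one scale.

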### Timetable:

Phase	Duration / Time Points	Description
Recruitment & Screening	1 month	Patient selection, informed consent, baseline assessment.
Baseline Assessment	Week 0	Initial evaluation of WSLs using Diagnodent Pen, digital photos, Gorelick Index, GBI, PI, and salivary pH.
Intervention & Follow-up	6 months	Participants receive assigned oral care regimen (toothpaste and mouthwash). Measurements at 1 month, 3 months, and 6 months for WSLs and oral health parameters.
Data Analysis	1 month	Statistical analysis of primary and secondary outcomes.

### Stopping Roles:

- Any patient developing severe adverse reactions to the products.

- Patient withdrawal of consent.

### **Budget and Funding:**

The study is self-funded

### **Ethical Approval:**

The protocol will be submitted to ethics committee

## **Data Management and Analysis**

### **Further Considerations**

#### **Pilot study:**

A pilot study will NOT be conducted

#### **Dissemination:**

Postgraduate Thesis

